3.4.2 Laboratory

Blood and urine samples will be used for determination of clinical chemistry, haematology and urinalysis parameters taken at scheduled time points as specified in Table 1, Section 4 of the CSP. The laboratory parameters to be measured are given in Table 3, Section 5.2.1 of the CSP. Laboratory data will be reported using Système International (SI) units.

Changes in haematology and clinical chemistry variables between baseline and each subsequent scheduled assessment will be calculated.

Absolute values will be compared to the relevant reference range and classified as low (below range), normal (within range or on limits) or high (above range). The central laboratory or local laboratory (for assessments measured at a local laboratory) reference ranges will be used for laboratory variables. All values (absolute and change) falling outside the reference ranges will be flagged.

Urinalysis data will be categorised as negative (0), trace, or positive (+) at each time-point and will be listed only.

For the purposes of haematology and clinical chemistry shift tables, baseline will be defined as the latest non-missing assessment prior to first dose, and during-study is as defined in [Section 3.4.1](#). Shift-tables will not be presented for the specific periods separately, i.e. ICS+LABA treatment period, ICS taper-down period or during the remainder of study. On treatment is defined as from date of first dose and including visit 14 (week 12).

For the liver function tests: Aspartate Aminotransferase (AST), Alanine Aminotransferase (ALT), Alkaline phosphatase (ALP) and total bilirubin (TBL), the multiple of the central or local laboratory upper limit of the normal (ULN) range will be calculated for each data point.

$$\text{Multiple} = \text{Value} / \text{ULN}$$

i.e. if the ALT value was 72 IU/L (ULN 36) then the multiple would be 2.

Patients who meet any of the following criteria at any point during the study will be flagged:

- $\text{AST} \geq 3\text{xULN}$
- $\text{ALT} \geq 3\text{xULN}$
- $\text{TBL} \geq 2\text{xUL}$

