1.3 Benefit/risk and ethical assessment

Asthma is a chronic inflammatory disorder of the airways associated with substantial morbidity. There are currently no available treatments shown to provide remission in asthma, but based on data gathered to date AstraZeneca considers AZD1419 to have the potential to induce long-term remission and disease control in asthmatics, removing the need for controller (maintenance) medication.

TLR9 agonists delivered as subcutaneous, intramuscular or intratumoral injection have been widely investigated in clinical studies, mainly for treatment of malignancies and as vaccine adjuvants, but also evaluated for treatment of asthma and allergic rhinitis. The most commonly reported adverse events are injection site reactions, flu-like symptoms (including headache, chills, fatigue, headache, myalgia and pyrexia) and in some cases hematological effects such as transient lymphopenia (Scheiermann J and Klinman DM 2014, Qin M et al 2014).

AZD1419 was not detected in any plasma sample from patients in the highest dose cohort (23.1 mg) in the previous trial and the systemic exposure in the proposed study, where the maximum given dose will be 8 mg, is expected to be low. The aim is to keep the sensitive parameter flu-like AEs at a low or absent level. Patients will start at 4 mg/week and based on occurrence of the flu-like symptoms in the individual patient, the dose will be maintained or adapted up or down. Should symptoms occur, they should be treated per standard medical practice (e.g. paracetamol) based on the judgment of the investigator.

TLR9 agonists could potentially, by inducing type 1 interferon production, aggravate or contribute to the development of autoimmune disease. To mitigate the potential risk for subsequent autoimmune reactions patients with a history of autoimmune disease will be excluded from taking part in the study. Transient increases in antinuclear antibodies (ANA) and anti-doublestranded DNA (anti-dsDNA) without clinical relevance have been seen upon CpG oligodeoxynucleotide (CpG ODN) (TLR9 agonist) and Interferon α (IFN- α) exposure. To increase our knowledge for the future clinical program patients will donate blood samples during the study for later analysis of selected auto-antibodies.

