3.4.5 Physical examination (not stated in the safety outcome measures)

Complete physical examinations will be performed at Visits 1 (Week -4), 6 (Week 4), 9 (Week 7), 15 (Week 13) and 21 (Week 52). Any new or aggravated existing finding(s) judged as clinically significant by the Investigator, at any post baseline physical examination during the study, compared to the screening (i.e. Visit 1) assessment will be reported as an AE.

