4.2.5.2 Laboratory data

All continuous laboratory parameters will be summarized by absolute value at each visit by treatment group, together with the corresponding changes from baseline. The summary statistics presented will be the minimum, 1st quartile, median, 3rd quartile, maximum, mean and SD. Mean changes from baseline over time will also be plotted by treatment group.

Central (or local) laboratory reference ranges will be used for the identification of individual clinically important abnormalities, and a shift table will be produced for each laboratory parameter to display low, normal, high, and missing values. The shift tables will present baseline and last on-treatment value for each parameter. On-treatment is defined from date of first dose and including visit 14 (week 12).

Shift plots showing each individual subject's laboratory value at baseline and at the last on-treatment value will be produced for each continuous laboratory variable. If any laboratory variables show any unusual features (high or low values or a general shift in the data points) at other time points, then shift plots of these data may be produced. A diagonal line indicating no change, and horizontal and vertical reference lines indicating the limits of the central (or local) laboratory reference ranges will also be displayed on the shift plots.

Data for subjects who have treatment-emergent changes outside predefined criteria will be presented. This data presentation will include all visits for this subset of subjects. A change is treatment-emergent if it occurred during treatment, from the date of first dose of randomised treatment up to and including the follow-up period.

The frequency of treatment-emergent changes outside predefined criteria between baseline and each post-treatment time point will be tabulated

In order to identify potential Hy's Law cases, maximum post baseline TBL will be plotted against maximum post baseline ALT, expressed as multiples of ULN. This plot will be repeated to show maximum post baseline TBL against maximum post baseline AST, expressed as multiples of ULN. These plots will be produced on a log scale and reference lines will be included at 2xULN for TBL and at 3xULN for ALT/AST.

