4.2.5.5 ECG

The Investigator's assessment of the 12-lead ECG (normal or abnormal) will be listed for all subjects, along with detailing whether any abnormalities were clinically significant or not.

A shift table will be produced showing the change between baseline and the end of study assessment.

Absolute values and change from baseline for ECG parameters RR, PR, QRS and heart rate reported by the central ECG laboratory will be summarized by visit. The reference ranges are presented in [Table 4](#).

Table 4 ECG reference ranges

| Parameter | Standard Units | Lower Limit | Upper Limit |
|------------------|-----------------------|--------------------|--------------------|
| ECG Heart rate | Beats/min | <60 | >100 |
| RR interval | ms | <60 | >100 |
| PR interval | ms | <120 | >200 |
| QRS duration | ms | <60 | >120 |

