4.2.5.6 Physical examination

Shift tables (normal, abnormal (same as baseline, new or aggravated)) of baseline versus last on-treatment observation will be generated, presenting the assessment for each component of the complete physical examination separately. Listings of abnormal results will be produced.

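### The physical examination shift table leaves out the Week 13 examination under either reading of on-treatment, and the RR limits in SAP Table 4 repeat the heart rate limits

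*SAP*

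**What the plan says.** **On-treatment.** SAP 3.4.2 states: "On treatment is defined as from date of first dose and including visit 14 (week 12". SAP 4.2.5.2 repeats it: "On-treatment is defined from date of first dose and including visit 14 (week 12". Both places concern laboratory data, and 4.2.5.2 adds: "The shift tables will present baseline and last on-treatment value for each parameter".

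**Physical examination.** SAP 4.2.5.6 says that shift tables "of baseline versus last on-treatment observation will be generated", without saying when treatment ends. SAP 3.4.5 gives the schedule: "Complete physical examinations will be performed at Visits 1 (Week -4), 6 (Week 4), 9 (Week 7), 15 (Week 13) and 21 (Week 52".

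**Link between the two.** SAP 3.4.1 lists the adverse event periods, the longest of which ends at Visit 21 (Week 52). It then says that laboratory and physical examination data share its during-treatment definition where applicable.

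**Visit windows.** SAP Table 6 gives Visit 14 (Week 12) a target of Day 85 and a window of Days 82-88. Visit 15 (Week 13) has a target of Day 99 and a window of Days 89-109.

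**ECG ranges.** SAP Table 4 contains the row "RR interval | ms | <60 | >100". The heart rate row above it has the same two limits in beats/min.

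**The concern.** The shift table is the only tabulated summary of physical examination in the SAP, and it uses one post-baseline value per patient. A reader will take that value as the state at the end of treatment. If it comes from Week 7, it precedes the last five doses and the whole period without controller medication. If it comes from Week 52, it is 40 weeks after the last dose. Protocol 1.3 reports that in monkeys immune-cell recruitment in the lungs persisted for at least 2 weeks after dosing and had resolved by 8 to 12 weeks. An examination soon after the last dose is therefore the one of most interest, and it is the one that the table omits.

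The RR row is a separate and simpler matter. A reference range that no living patient can meet cannot distinguish normal from abnormal.

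**Working it through.** **Inputs.** Examinations after the first dose are at Weeks 4, 7, 13 and 52 (SAP 3.4.5). There are 13 weekly doses, at Weeks 0 to 12 (SAP 4.2.3.1). Controllers are fully withdrawn before dose 10 (Protocol 4.2). Windows are from SAP Table 6, and heart rate and RR limits from SAP Table 4.

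**Numbering.** For Visits 2 to 14, visit n falls at Week n − 2 and carries dose n − 1. Visit 9 is Week 7 (dose 8), and Visit 14 is Week 12 (dose 13). The target day is 7 × week + 1, so Visit 9 is Day 50 and Visit 14 is Day 85.

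**Last on-treatment examination, Week 12 reading**

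1. Scheduled examinations at or before Week 12 are Weeks 4 and 7, so the last is Week 7 (Visit 9). The Visit 14 window ends on Day 88. The Week 13 examination falls in Days 89-109 and cannot be drawn in.
2. Doses still to come after the Visit 9 dose: 13 − 8 = 5, and 5/13 = 38%. They include all four doses given without controllers (10 to 13).
3. Time from that examination to the last dose: 85 − 50 = 35 days.

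**Last on-treatment examination, Visit 21 reading**

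4. A completer's last examination is Week 52, Day 365. That is 365 − 85 = 280 days, or 40 weeks, after the last dose. Week 13 is again not the value shown.

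**Visit 15 target day**

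5. Week 13 should be 7 × 13 + 1 = Day 92. Table 6 says Day 99, which is 99 − 85 = 14 days after dose 13. The other 19 rows of Table 6 fit the rule.
6. The exposure formula in SAP 4.2.3.1 gives (85 + 7) − 1 + 1 = 92 days for full dosing, so exposure ends on Day 92, before the Day 99 target.
7. Taking in the whole Visit 15 window moves the cut-off from Day 88 to Day 109: 109 − 88 = 21 days.

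**RR limits.** RR (ms) = 60000 / heart rate (beats/min).

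| Starting value | Converts to |
|---|---|
| 60 beats/min | 1000 ms |
| 100 beats/min | 600 ms |
| 60 ms | 1000 beats/min |
| 100 ms | 600 beats/min |
| 30 to 250 beats/min | 2000 to 240 ms |

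The stated range of 60-100 ms cannot be reproduced from the heart rate row, which implies 600-1000 ms. Every RR value for heart rates of 30 to 250 beats/min exceeds 100 ms and would be classed as high.

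**The case against.** **The Week 12 cut-off is laboratory text.** Applying it to physical examination is an inference, and a reader might go too far in stating Week 7 as settled. This stands: strictly, the term is undefined for that table. Week 12 is still the more natural reading, because 3.4.2 treats during-study and on-treatment as different terms and no other definition of on-treatment exists. Week 13 is lost to a completer under both readings.

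**Not every patient is a completer.** An unscheduled or early-exit examination could fall between Week 7 and Week 12. Under the Visit 21 reading, a patient who leaves before Week 52 could have Week 13 as the last value. This also stands.

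**The findings are not lost.** A reader might infer that late-dosing findings vanish from the report. They do not. SAP 4.2.5.6 lists abnormal results, and SAP 3.4.5 sends new or aggravated clinically significant findings to adverse event reporting. Protocol 8.5.9.4 plans examination summaries by visit, and SAP section 6 records no removal of them. The fault is in one table.

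**Laboratory shifts.** A reader might infer that a last-value shift would hide the "hematological effects such as transient lymphopenia" mentioned in Protocol 1.3. The documents do not support this as an error. That text concerns injected drugs of the class and reports the effect only in some cases. SAP 3.4.2 flags every out-of-range value. SAP 4.2.5.2 also plans by-visit summaries with minimum and maximum, plots of mean change, and treatment-emergent change displays that run through follow-up.

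**Internal contradiction.** The exposure formula and the flu-like event period in SAP 4.2.5.1 run past Week 12, which might suggest that the SAP contradicts itself. This is weak. SAP 4.2.3.1 itself ends dosing at Week 12, and the flu-like period stops before Visit 15.

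**ECG.** It would be wrong to say that every ECG is out of range, since only the RR row is affected. The SAP sets out no step that flags ECG values against Table 4.

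**Conclusion.** Two limited points hold.

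1. The physical examination shift table rests on an undefined term. For a completer with scheduled examinations only, it shows Week 7 (before 5 of 13 doses) or Week 52 (40 weeks after the last dose), and never Week 13. One summary table is affected and no data are lost. The same would apply to the laboratory shift tables only if a panel is scheduled at Visit 15, which cannot be read from the available copy of Protocol Table 1.
2. The RR limits in Table 4 are clerical errors that would class every plausible RR value as high. RR means and changes from baseline are unaffected. The harm arises only if the limits are used to flag or categorise values.

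The use of last value in the laboratory shift tables is not an error. A lowest and highest value shift would be an optional addition.

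**What to change.** - Define on-treatment once, in the SAP's general principles, for the physical examination shift table and for the laboratory shift tables if a panel is scheduled at Visit 15. Name Visit 15 (Week 13) as included. A cut-off of last dose plus 7 days alone is not enough, because it ends on Day 92 while Table 6 targets Visit 15 at Day 99.
- Show the Week 52 examination as a separate shift.
- Reconcile Visit 15's Table 6 target of Day 99 with its Week 13 label (Day 92).
- Make the RR row agree with the heart rate row: below 600 and above 1000 ms if 60-100 beats/min is kept. SAP Table 2 uses 50-100 beats/min for pulse. If 50 were adopted as the lower heart rate limit for ECG, the upper RR limit would be 60000/50 = 1200 ms, so the SAP should state which it intends.

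The cost is SAP wording and table programming, with no new data. The drawback is a later on-treatment cut-off for these tables: Day 109 at the latest in place of Day 88, up to 21 days.

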3.4.3 Vital signs

Vital sign assessments (pulse, systolic blood pressure, diastolic blood pressure and pulse oximetry), will be performed as in accordance with the schedule provided in [Table 2](#), Section 4 in the CSP. Height and weight will be assessed at screening only.

Change from baseline in vital signs will be calculated for each post-randomisation visit.

Absolute values for vital signs will be compared to the relevant reference ranges and classified as low (below range), normal (within range or on limits of range) and high (above range). All values (absolute and change) falling outside the reference ranges will be flagged.

Body mass index will be calculated from the height (in meters) and weight (in kilograms) as follows:

$$BMI = kg/m^2$$

Table 2 Vital signs reference ranges

| Parameter | Standard Units | Lower Limit | Upper Limit | Change Criteria |
|------------------------------|----------------|-------------|-------------|-----------------|
| Diastolic Blood Pressure* | mmHg | <60 | >100 | ±15 |
| Systolic Blood Pressure* | mmHg | <90 | >160 | ±30 |
| Pulse* | Beats/min | <50 | >100 | ±20 |
| Peripheral Oxygen Saturation | % | <90 | =100 | N/A |

* Will be taken lying down

3.4.4 Electrocardiograms (ECG)

Twelve-lead ECG measurements will be recorded in accordance with the protocol at screening and at the safety follow-up visit at the end of the trial.

The outcome of the overall evaluation is to be recorded as normal/abnormal in the eCRF, with any abnormalities being recorded as not clinically significant or clinically significant.

Abnormal values shall not be recorded as AEs unless deemed clinically significant. The printout of the ECG is to be signed, dated and filed in the Investigator study file along with a signed and dated copy (if the printouts are not on archive-quality paper).

The reference ranges for the ECG tests are presented in [Table 4](#).

3.4.5 Physical examination (not stated in the safety outcome measures)

Complete physical examinations will be performed at Visits 1 (Week -4), 6 (Week 4), 9 (Week 7), 15 (Week 13) and 21 (Week 52). Any new or aggravated existing finding(s) judged as clinically significant by the Investigator, at any post baseline physical examination during the study, compared to the screening (i.e. Visit 1) assessment will be reported as an AE.

3.4.6 Diffusing Capacity of the Lung for Carbon Monoxide

Measurement of the diffusing capacity of the lung for carbon monoxide (DLco) will be performed at Visits 1 (Week -4), 2 (Week 0), 6 (Week 4), 9 (Week 7), 15 (Week 13) and 17 (Week 20).

3.5 Calculation or derivation of exploratory endpoints

3.5.1 Composite endpoint for exacerbations (CompEx)

CompEx ([Anne L Fuhlbrigge et al. 2017](#)) will be assessed in two ways: (i) as time to first CompEx event during the 52-weeks following randomisation and (ii) as proportion of patients with a CompEx event during the 52-weeks following randomisation.

A CompEx event is defined as the first occurrence of either a diary event or a severe exacerbation.

For the development of CompEx, the following diary variables are particular of interests: peak expiratory flow (P), reliever medication use (R), asthma symptoms (S) and night-time awakening (A). Diary events for the purpose of this study, which must include peak expiratory flow (P), are defined as either at least two variables fulfilling threshold criteria, or at least one variable fulfilling a threshold criterion and the slopes for all variables fulfilling the slope criteria.

Deterioration criteria for the individual diary event are defined as either changes from baseline, larger than a pre-specified threshold for at least 2 consecutive days, or as a worsening greater than a certain magnitude (slope) over at least 5 days.

The baseline levels of deterioration should be calculated for each individual as the mean over the 5 days ending just before the day of randomisation for each of the diary variables (they do not have to be 5 consecutive days). If <5 days data are available, then take the mean for the number of days where data is collected, and if missing, the first 3 days after randomisation should be used. No imputation of missing diary data after randomisation should be performed.

Five variants of CompEx (based on diary records Peak expiratory flow and Reliever medication use (PR); Peak expiratory flow and Symptoms (PS); Peak expiratory flow and Awakenings (PA); Peak expiratory flow, Reliever medication use and Symptoms (PRS) and Peak expiratory flow, Reliever medication use, Symptoms and Awakenings (PRSA) respectively) will be explored and are defined in [Table 3](#) along with criteria for events in term of thresholds and slopes. PRS is pre-specified to be the primary diary event endpoint of interest.

A diary event required the fulfilment of at least two worsening criteria defined as:

1. at least two variables fulfilling threshold criteria; or

2. at least one variable fulfilling a threshold criterion and the slopes for all variables fulfilling the slope criteria.

The occurrence of a diary event within a subject is defined as the first occasion when either (1) or (2) above occurs. For example, in the case of the algorithm for the PRS diary event defined in [Table 3](#): this diary event is based on PEF [morning (m) and evening (e)], reliever use [morning and evening] and symptoms [morning and evening], giving six different diary variables to consider. The diary event for case (1) is defined so that the threshold deterioration criterion needs to be fulfilled for one of the PEF variables at the same time as the criterion is fulfilled for either one of the reliever or symptom variables. This gives in total eight variable combinations (Pm/Rm, Pm/Re, Pe/Rm, Pe/Re and Pm/Sm, Pm/Se, Pe/Sm, Pe/Se) where the deterioration needs to be fulfilled for both variables in at least one combination in order for a diary event to occur. The first of the two days where the threshold is reached for at least two variable is taken as the starting point of the event.

The diary event for (2) will occur when one of the six diary variables fulfils the threshold deterioration criterion at the same time as the slope criterion is fulfilled for all six variables.

The thresholds (as T1 in the reference paper) for the diary event endpoints are defined as follows:

- PEF morning/evening: $\geq 15\%$ decrease compared to baseline
- Reliever medication (rescue) use morning/evening: increase ≥ 1.5 doses compared to baseline
- Asthma symptoms morning/evening: increase of ≥ 1 score compared to baseline or absolute score of 4
- Night-time awakening: awakening with increase in rescue use (> 0.5 doses) relative to baseline

The slopes (as S3 in the reference paper) for the diary event endpoints are defined as follows:

- PEF morning/evening: decrease rate $> 3\%$ per day
- Reliever medication (rescue) use morning/evening: increase rate > 0.3 doses per day
- Asthma symptoms morning/evening: increase rate > 0.2 scores per day
- Night-time awakening: increase rate > 0.1 doses per day

The following is an illustrative example for calculating the slope for PEF (evening):

- Fit a univariate linear regression line $y = k*x + m$

- where y = PEF change from baseline (evening), x = day, k = slope and m = intercept

Slopes are computed over 5-day intervals with the last day of the interval being the start day of the event. If there is less than 2 days with available data in an interval, slope is set to missing and the condition is not fulfilled. Thresholds are computed for 2-day intervals with the first day of the interval being the start day of the event.

Threshold diary events are defined as starting at the earliest on the start day of treatment (Day 1), with event on Days 1-2, and at the latest ending on Day 364 (event on Days 364-365).

Slope diary events (start day of treatment = Day1) are defined as starting at the earliest on Day 5 (with event on Days 1-5) and ending latest on Day 365 (with event on Days 361-365). However, if slope diary events are calculated for those days where at least one variable fulfills a threshold criterion, the last possible day for a slope diary event will be Day 364.

For subjects prematurely discontinuing, the above definitions will be amended for actual end day of treatment and actual start day of post-treatment.

Events are searched for up to the last day with entry in the diary cards. Missing values indicate no event. Missing diary data will not be imputed. If diary card entries stop prematurely (before the last day in the study) or if the patient lacks data during the period, the patient is to be censored as having no event at the last day in the period. This will be either the last day with recordings in the diary or the last day the patient was assessed for severe asthma exacerbation.

The outcome variables for CompEx events will be as follows:

- Time to first CompEx event during the 52-weeks following randomisation, for each of CompEx PR, PS, PA, PRS and PRSA
- Proportion of patients with a CompEx event during the 52-weeks following randomisation, for each of CompEx PR, PS,PA, PRS and PRSA

Table 3 Definition of diary events evaluated as possible building blocks for CompEx

| Diary event | Variables | Definition |
|-------------|---|--|
| PR | P - PEF morning/evening R - Reliever morning/evening | 2/2 days above threshold on PEF (morning or evening) and reliever (morning or evening), or 2/2 days above threshold on 1/4 variables + 4/4 slopes |
| PS | P - PEF morning/evening S - Symptoms morning/evening | 2/2 days above threshold on PEF (morning or evening) and symptoms (morning or evening), or 2/2 days above threshold on 1/4 variables + 4/4 slopes |
| PA | P - PEF morning/evening A - Awakenings + Reliever morning | 2/2 days above threshold on PEF (morning or evening) and awakenings, or 2/2 days above threshold on 1/3 variables + 3/3 slopes |
| PRS | P - PEF morning/evening R - Reliever morning/evening S - Symptoms morning/evening | 2/2 days above threshold on PEF (morning or evening) and [reliever (morning or evening), or symptoms (morning or evening)], or 2/2 days above threshold on 1/6 variables + 6/6 slopes |
| PRSA | P - PEF morning/evening R - Reliever morning/evening S - Symptoms morning/evening A - Awakenings | 2/2 days above threshold on PEF (morning or evening) and [reliever (morning/evening), or symptoms (morning or evening), or awakenings (with reliever morning increased)], or 2/2 days above threshold on 1/7 variables + 7/7 slopes |

Abbreviations: PEF: peak expiratory flow; R: reliever use (doses); A: awakenings + morning reliever use; S: symptoms

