4.3 Follow-up period/Observation period

After the treatment period patients are followed until they experience loss of asthma control or for the whole period of up to 52 weeks (Visit 21). For details of the study assessments during the observation period refer to the Schedule of events, Table 1.

Patients will be monitored with regards to safety, tolerability and efficacy aspects during the whole study period. In addition to assessments performed at the clinical visits, an ePRO device coupled with a home spirometer will on a daily basis capture asthma symptoms, reliever use and lung function (PEF) and a FeNO meter measurements will be performed every second day.

At any time during the tapering period or after, when patients experience loss of asthma control as defined below, they will resume their usual ICS+LABA asthma controller therapy and will be considered to have reached the primary endpoint. They will then stop IMP administration and will be followed for an additional 4 weeks in the study.

For the purpose of the study Loss of asthma control is defined as any of the following:

- a) An increase of ACQ-5 to 1.5 or more
- b) A reduction of 30% or more in morning peak expiratory flow (PEF) from baseline on 2 consecutive days
- c) At least six additional reliever inhalations of SABA in a 24-hour period relative to baseline on 2 consecutive days
- d) An exacerbation requiring systemic corticosteroids

Upon a), b) or c) being fulfilled, an automatic asthma action plan will be triggered in the ePRO device prompting the patient to resume their usual ICS + LABA medication. In addition an alert will be sent to the site/Investigator. Upon receiving such an alert the Investigator should contact the patient and arrange a visit to the clinic for evaluation, see Section 5.1.3.1. Blood sampling for biomarkers should be part of this evaluation.

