4. ANALYSIS METHODS

4.1 General principles

The analysis of the study outcome variables will include all data captured during the 52-week double blind treatment and follow-up period. This includes data regardless of whether IP was prematurely discontinued or delayed, and/or irrespective of protocol adherence, unless the patient withdraws consent or assent to study participation.

A summary table which counts patients who have been incorrectly randomised and who received incorrect treatment will be presented.

Summary data will be presented in tabular format by treatment. Categorical data will be summarized by the number and percentage of patients in each category. Continuous variables for parametric data will be summarized by descriptive statistics including N, mean, (standard deviation) SD, median, and range.

Minimum and maximum values will be reported to the same degree of precision as the raw data unless otherwise stated. Mean, median, SD, confidence intervals (CIs), geometric mean and CV will be reported to one further degree of precision. Percentage frequencies will be presented to one decimal place.

Given the number of endpoints in the secondary analyses, multiplicity procedures will not be used to attempt to control 'alpha' across all secondary endpoints.

All data will be listed. Data listings will be sorted by treatment and subject number. Summaries by visit will include baseline but not visits intended for screening and randomisation.

All hypothesis testing will be reported using 2-sided tests except for the primary analysis which will be 1-sided and the p-value will be presented to 4 decimal places. Where confidence

intervals (CI) are presented for treatment comparisons these will be presented as 2-sided 95% CIs.

Plots of data by visit or visit window will cover the entire study period including follow-up.

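### SAP 3.5.1 gives conflicting rules for where the exploratory CompEx diary search ends; on one reading, stopping IP at loss of control in Weeks 6–12 removes the accompanying event

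*SAP*

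**What the plan says.** SAP 3.5.1 defines the composite: "A CompEx event is defined as the first occurrence of either a diary event or a severe exacerbation". It is analysed as time to first event and "as proportion of patients with a CompEx event during the 52-weeks following randomisation". Threshold diary events can start from Day 1 to Day 364, and slope events can end as late as Day 365. Then comes the sentence at issue: "For subjects prematurely discontinuing, the above definitions will be amended for actual end day of treatment and actual start day of post-treatment". The paragraph after it reads: "Events are searched for up to the last day with entry in the diary cards". That paragraph censors at the last diary recording or the last assessment for severe exacerbation, with no exception for patients who stop IP.

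SAP 4.1, on the data used for all outcome variables, says: "This includes data regardless of whether IP was prematurely discontinued or delayed, and/or irrespective of protocol adherence".

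Protocol 4.3 deals with loss of asthma control during the taper or later: "They will then stop IMP administration and will be followed for an additional 4 weeks in the study". The taper starts at dose 7, Week 6 (Protocol 4.2). Dosing ends at Week 12 after at most 13 weekly doses (SAP 4.2.3.1).

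**The concern.** The window sentence would suit a trial in which treatment and observation end together. Here a patient who completes dosing at Week 12 is still searched for up to about 40 weeks after the last dose. If the amendment means the end of IP, only patients who stop IP early have their window cut. From Week 6 onward, a main reason for stopping is loss of control, which is closely related to the CompEx event.

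With weekly dosing, the last dose precedes the deterioration that ended dosing. A cut at the last dosing date would therefore censor that patient as event-free just before the event. The length of the search would depend on the outcome. If the drug works, this would happen more often on placebo. At stake are the CompEx event count, the ratio of proportions and the power of the CompEx comparisons in SAP 4.2.5.7.

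**Working it through.** **1. The plan's own figure.** There is no sample-size statement for CompEx. For the primary endpoint, Protocol 8.2 gives 20% versus 60% controlled at Week 52, two-sided alpha 0.05, about 90% power and 32 events. Under proportional hazards, HR = ln 0.6 / ln 0.2 = 0.317 and |ln HR| = 1.148. Schoenfeld: events = 4 × (1.960 + 1.282)² / 1.148² = 31.9, so 32. Power with 32 events is 90.1%. The figure reproduces, and the same rates are used below.

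**2. What the end day could be.** The SAP supports several candidates:
- the last dosing date (plain reading of end of IP);
- last dosing date + 7 days (exposure formula, SAP 4.2.3.1);
- Visit 14, Week 12 (the laboratory on-treatment rule, SAP 3.4.2 and 4.2.5.2);
- the end of the 52 weeks, which SAP 3.3.1 and 4.2.4 also call the treatment period.

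**3. Size if the last dosing date is used.** Inputs: 81 randomised (SAP 1.3) at 1:1, taken as 41 placebo and 40 active. Assumptions not in the documents: 70% of losses of control come with a CompEx event, its onset is on the same date, and the hazard has the shape shown. Only losses in Weeks 6–12 are cut, because the IP stop in Protocol 4.3 applies from the taper.

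Without a cut, placebo has 0.7 × 41 × 0.80 = 23.0 events and active 0.7 × 40 × 0.40 = 11.2, total 34.2. Power = Φ(√(34.2/4) × 1.148 − 1.960) = 92%. The ratio of proportions is 0.40/0.80 = 0.50.

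With a hazard constant from week s, the probability of loss in Weeks 6–12 is exp(−λ(6 − s)) − exp(−λ(12 − s)), where λ = −ln S(52)/(52 − s).

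| | Hazard from Week 6 | Hazard from Week 0 |
|---|---|---|
| Probability of loss in Weeks 6–12, placebo / active | 0.189 / 0.064 | 0.141 / 0.054 |
| Events removed, placebo (0.7 × 41 × p) | 5.4 | 4.0 |
| Events removed, active (0.7 × 40 × p) | 1.8 | 1.5 |
| Events left, total | 26.9 | 28.6 |
| Power (Schoenfeld) | 85% | 87% |
| Ratio of proportions | (0.400 − 0.064)/(0.800 − 0.189) = 0.55 | (0.400 − 0.054)/(0.800 − 0.141) = 0.52–0.53 |

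Simulation of 41 versus 40 patients agrees: power about 91% uncut and 84–87% cut, with 4 to 6 placebo events and about 2 active events removed.

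**4. Cox hazard ratio.** A simulation with 3,000 per arm, hazard from Week 6 and all losses accompanied gave HR 0.316 with the cut and 0.313 without. This is expected. Under proportional hazards, removing the events of Weeks 6–12 leaves the later weeks to estimate the same ratio, with fewer events.

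**5. Other end days.** In the same simulation a cut at last dose + 7 days removed no events, because the next weekly dose would have been due by then. A window ending at 52 weeks removes none either.

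**6. Sensitivity to clustering.** If 25–50% of the 52-week cumulative hazard fell in Weeks 6–12, the cut at the last dosing date would remove the event in 33–55% of placebo and 12–22% of active patients when every loss is accompanied. The ratio of proportions would be 0.60–0.71. The documents give no hazard shape, so this is a range and not an estimate.

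**The case against.** A reader might infer that the search **is** cut at the last dose for early discontinuers and runs to Day 364 for everyone else. The documents do not establish that. The sentence amends definitions that run to Day 364/365, and the SAP repeatedly calls the whole 52 weeks treatment. On that usage, discontinuing prematurely means leaving the study, and nothing is cut at the last dose. The next paragraph and SAP 4.1 also point the other way. Nor is everyone else searched to Day 364: patients who lose control after dosing leave four weeks later, so their search ends at their last diary day.

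This stands against any claim that events will be dropped. It does not remove the conflict. SAP 4.1, 4.2.2 and 4.2.3.1 use the same discontinuation wording for IP, while SAP 2.1.2 uses it for the study. The sentence also separates treatment from post-treatment. A programmer could reasonably apply the cut, and nothing says which rule prevails.

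Other limits also stand:
- A reader might expect time to first CompEx to be biased toward no difference. The specified analysis is a Cox model, and its HR hardly moves. Only the ratio of proportions is diluted.
- Cutting losses in Weeks 0–6 as well would bring power to about 77% by the same formula (34.2 − 8.9 − 3.1 = 22.1 events). Protocol 4.3 does not support that case.
- CompEx thresholds (15% PEF fall, 1.5 doses) are lower than the loss-of-control limits (30%, six inhalations). Some diary events would start before the last dose and survive the cut, so same-date onset is pessimistic.
- The sentence does not name the severe-exacerbation component.
- The excess loss on placebo assumes that the drug works. With no effect, the loss is balanced.

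**Conclusion.** The point holds as a conflict between rules, with undefined terms, in an exploratory endpoint. SAP 3.5.1 leaves open whether stopping IP ends the CompEx diary search, and the answer matters because loss of control in Weeks 6–12 itself stops IP.

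The loss in step 3 arises only if the end day is read as the last dosing date, and it rests on the planning rates, 70% accompaniment, same-date onset and a constant hazard. It would be larger if losses cluster just after withdrawal and smaller if diary events start before the last dose. It is zero if the end day is last dose plus 7 days or the end of the 52 weeks. The primary and secondary analyses are untouched. Severity: minor.

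**What to change.** Delete the sentence on subjects prematurely discontinuing from SAP 3.5.1. Alternatively, replace it with a statement that stopping IP does not shorten the search, and that CompEx events are searched from Day 1 to the earlier of (a) Day 364/365 and (b) the last diary day or last severe-exacerbation assessment. This agrees with the following paragraph, the 52-week outcome and SAP 4.1. It costs one SAP sentence and needs no new data. It should be settled before unblinding, the point by which Protocol section 8 requires final SAP amendments.
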